After IC is obtained, participants will be asked to complete the two self-report measures on psychological distress (K10) and daily functioning (WHODAS 2.0). Participants who meet the inclusion criteria will be assessed for suicidal ideation (PM+ manual suicidal thoughts interview) and severe disorders (PM+ manual observation checklist). The independent assessors will refer individuals meeting any of the exclusion criteria to specialist support according to their needs.

Participants who meet all inclusion criteria will complete the baseline assessment at the same visit. This involves questionnaires on depression and anxiety (25-item Hopkins Symptoms Checklist; HSCL-25), trauma exposure (Trauma Experiences checklist), daily

stressors (Post-Migration Living Difficulties; PMLD), posttraumatic stress (PTSD Checklist for DSM-5; PCL-5), self-identified problems (Psychological Outcomes Profiles; PSYCHLOPS), anger (Trait Anger Scale; STAS-T), and questions on access to health services. Furthermore, the assessor will administer a health service utilisation and productivity impact interview (locally adapted version of the Client Service Receipt Inventory; CSRI).

The post-assessment (WHODAS 2.0, HSCL-25, PMLD, PCL-5, PSYCHLOPS, CSRI) is scheduled 6 weeks after the baseline assessment (or 1 week after the 5th PM+ session). The follow-up assessments are scheduled 3 months after the 5th PM+ session (WHODAS 2.0, HSCL-25, PMLD, PCL-5, PSYCHLOPS, STAS-T, CSRI) and 12 months after baseline (all 3-month follow-up measures and the Traumatic Experiences checklist, except the STAS-T). We also measure hair cortisol concentrations (HCC) at baseline and 3-month follow-up to investigate the effect of PM+ on HCC.

All questionnaires, except the exclusion instruments (the PM+ manual's suicidal thoughts interview and assessment tool for severe disorders) and the CSRI interview are self-administered on a tablet with audio functions (cf. Morina et al., 2017). Independent Arabic-speaking assessors with at least a degree-level will carry out the assessments. Assessors will receive a three-day training on the administration of questionnaires, use of the tablets, general interview techniques, common mental disorders, psychological first aid and ethical research conduct. The assessors are blinded to treatment allocation.

Sample size

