Power calculations were carried out by the VUmc Department of Epidemiology and Biostatistics. Based on previous RCTs on PM+ (Bryant et al., 2017; Rahman et al., 2016), we aim for a conservatively estimated small to medium Cohen's *d* effect size of 0.4 in the PM+ group at 3-months follow-up. Power calculations suggest a minimum sample size of 133

participants per group (power = 0.90, α = 0.05, two-sided). Taking into account an expected 30% attrition rate at the 3-month follow-up, we aim to include a total number of 380 participants (190 in the CAU/PM+ group and 190 in the CAU group).

Randomization

After baseline, participants will be randomized into the CAU/PM+ group or CAU group. Permuted blocks randomization will be performed using computerized software on a 1:1 basis and by means of sealed opaque envelopes. Household members will be randomized together to decrease the risk of contamination. The first PM+ session will be scheduled within one week after the baseline assessment.

Problem Management Plus (PM+)

We will test individual PM+ delivered by Syrian peer-refugees. During this 5-week intervention, a new treatment strategy is introduced in every session and subsequently reviewed in all following sessions. Stress management is practiced in session 1 using a slow breathing exercise. Problem management is taught in session 2 using a step-by-step plan to pro-actively manage practical problems. Behavioral activation is introduced in session 3 by encouraging the participant to re-engage with pleasant and task-oriented activities. Strategies to strengthen social support are discussed in session 4. Homework assignments are carried out between the sessions and relapse prevention strategies are discussed in session five (Dawson et al., 2015; Sijbrandij et al., 2017).

The adaptation of the PM+ intervention and development of training materials was coordinated by the Danish Red Cross in collaboration with the WHO and partners in STRENGTHS. Adaptations were made according to a framework for the cultural adaptation of psychological interventions (Bernal & Sáez-Santiago, 2006), and involved a literal

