sessions for protocol adherence purposes. A random sample of 10% of the audio recordings will be coded by an independent researcher with in-depth knowledge of PM+. Helpers will complete fidelity checklists addressing the PM+ components during the sessions (cf. Bryant et al., 2017; Rahman et al., 2016).

Trial monitoring and adverse events reporting

The VU research team has full access to the trial dataset. Adverse events (AE) or serious adverse events (SAE) are defined as any undesirable experience occurring to a participant during the study, whether or not considered related to the trial procedure or the PM+ intervention. All SAEs will be recorded in Castor EDC trial monitoring software (Ciwit BV, 2018) and reported to the SB and to the Central Committee on Research Involving Human Subjects within 7 days (in case of death or life-threatening situation) or 15 days (all other SAEs) after being informed about the event. SAEs will be followed-up until they have abated or until a stable situation has been reached, and if necessary, referral to a general physician will be made.

Analysis

To measure comparisons at baseline between the two treatment groups, t-test (continuous variables) or chi-square tests (categorical variables) will be conducted for normally distributed data; Mann-Whitney tests will be conducted for continuous non-normally distributed data.

Both intention-to-treat (ITT) analysis, including all randomized participants ($N=380$), and completers' analysis will be carried out. The main conclusion will be based on the ITT analysis. To estimate the treatment effect, a linear mixed model will be employed for the primary endpoint analysis, which will have treatment as fixed effects, baseline measurement of primary endpoint as covariate, and subject as random effects. The mean difference between

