the two arms at each assessment with its 95% confidence interval will be derived from the mixed model. The effects of PM+ on secondary outcomes (i.e., functional impairment, symptoms of PTSD, self-identified problems, anger, health and productivity costs, and HCC) will be examined using linear mixed models with treatment as fixed effects, baseline measurement as covariate, and subject as random effects. Covariate-adjusted mixed model of primary endpoint will also be performed by adding relevant covariates at baseline (e.g., gender, age, education, baseline levels of depression, anxiety, PTSD, traumatic experiences, post-migration living difficulties, and HCC hypo- versus hypersecretion, etc.) to the above-mentioned model.

For the economic analysis incremental cost-effectiveness ratios (ICERs) will be generated comparing changes in mean costs and primary outcomes from a payer and societal perspective between the two arms. Non-parametric bootstrapping analyses to derive 95% confidence intervals around ICERs , and cost-effectiveness acceptability curves will be generated showing the likelihood that PM+ would be cost-effective at different willingness-to-pay thresholds.

Descriptive analyses will be carried out in SPSS and hierarchical linear modeling analyses in R version 3.6.0. Across all analyses, two-tailed tests will be reported with $p < 0.05$.

Interview transcripts from the process evaluation will be analyzed thematically following the framework approach (Pope, Ziebland, Mays, & Mays, 2000) using NVivo version 11 (QSR International Pty Ltd, 2015).

Discussion

In this RCT we aim to evaluate the effectiveness and cost-effectiveness of the peer-refugee delivered PM+ intervention among Syrian refugees in the Netherlands impaired by symptoms

of psychological distress. Within the larger STRENGTHS project, other RCTs with different modes of delivery (see Sijbrandij et al., 2017) will be conducted among Syrian refugees in Europe and the Middle East, which will strengthen external validity of trial findings and provide a potential model for scaling up in both high- and low-income settings.

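### On its ordinary reading, the subject-only random effect assumes equal variances and correlations over visits at about weeks 6, 18 and 52; this can shift the 3-month effect under arm-dependent dropout and miscalibrate the intervals at individual visits

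*Protocol*

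**What the plan says.** The Analysis section of the protocol gives the primary model as a linear mixed model "which will have treatment as fixed effects, baseline measurement of primary endpoint as covariate, and subject as random effects". The secondary outcomes get "linear mixed models with treatment as fixed effects, baseline measurement as covariate, and subject as random effects". No random slope, residual covariance, visit-specific variance or robust standard error is named. The difference between "the two arms at each assessment with its 95% confidence interval will be derived from the mixed model", so a single model has to serve all post-baseline visits.

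The Procedure section sets the schedule. The post-assessment "is scheduled 6 weeks after the baseline assessment". "The follow-up assessments are scheduled 3 months after the 5th PM+ session", and the last visit falls 12 months after baseline. Hair cortisol (HCC) is measured at baseline and 3-month follow-up only. The trait anger scale (STAS-T) is not in the post-assessment list and is excluded at 12 months.

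The Sample size section allows for an "expected 30% attrition rate at the 3-month follow-up". It does not split attrition by arm or relate it to outcome. The main conclusion rests on the intention-to-treat analysis of all 380 randomised participants.

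**The concern.** A random intercept with independent, equal-variance residuals is compound symmetry: the same variance at every visit and the same correlation between any two. The visits are about 12 and 34 weeks apart, and nothing in the protocol suggests that scores that far apart are equally correlated or equally spread.

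Two results depend on this. First, the protocol names no other method for missing data, so the likelihood recovers information on participants lost at 3 months from their post-assessment score, through the assumed covariance. With 30% expected missing at the primary visit, a wrong covariance can move the primary contrast. Second, the interval at each visit uses a variance pooled over visits, so it has the wrong width wherever the visit's own variance differs from the average.

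This is separate from the absence of visit and treatment-by-visit terms in the stated model. Adding those terms does not change the covariance; the calculations below already include them.

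**Working it through.** **The plan's own figure.** For d = 0.4, power 0.90 and two-sided α = 0.05, the normal approximation gives 2(1.960 + 1.282)²/0.4² = 131.3, so 132 per group. The exact noncentral-t calculation gives 133 (power 0.901). Then 133/0.70 = 190 per group and 380 in total. The stated sample size is reproduced and is not affected by this point.

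**Visit times (Randomization and Procedure sections).** Session 1 is within a week of baseline and the five sessions are weekly, so session 5 falls at about week 5. The post-assessment is then at about week 6, the 3-month visit at about 5 + 13 = week 18, and the last visit at week 52. The gaps are 12 and 34 weeks.

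**3-month bias.** Let Y1 be the post-assessment score and Y2 the 3-month score, with dropout after Y1 depending on Y1. The model fills in Y2 with slope b, while the true slope is β. With visit-by-arm means in the model,

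bias = (β − b) × Δ,

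where Δ is the PM+ minus CAU difference in (mean Y1 among those retained − mean Y1 among all). For true SDs s1, s2, s3, β = r12·s2/s1. Under compound symmetry b is approximately the mean covariance divided by the mean variance. The bias is therefore zero if the covariance is exchangeable (β = b) or if selection is the same in both arms (Δ = 0). Its sign is the sign of (β − b)Δ.

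**Assumptions (none are in the protocol).** Scores are scaled to SD 1 at 3 months, with a true effect of −0.4 at the post-assessment and at 3 months. In the moderate arm-dependent setting, the log-odds of dropout after the post-assessment are −1.0 + 0.5·Y1 in CAU and −0.9 − 0.5·Y1 in PM+, which retains 72% and 66% at 3 months. Δ comes from integrating over Y1.

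Example, row C: β = 0.65 × 1.0/0.85 = 0.765. Mean covariance = (0.5525 + 0.600 + 0.357)/3 = 0.503, mean variance = (0.7225 + 1 + 1.44)/3 = 1.054, so b = 0.477. Bias = (0.765 − 0.477) × 0.214 = 0.062.

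| Row: SDs; r12, r23, r13 | β | b | Δ | (β − b)Δ | Simulated bias | 3-month coverage |
|---|---|---|---|---|---|---|
| A: 1/1/1; 0.50, 0.50, 0.50 | 0.50 | 0.50 | 0.295 | 0 | 0.000 | 95% |
| B: 1/1/1; 0.65, 0.50, 0.35 | 0.65 | 0.50 | 0.295 | 0.044 | 0.044 (11%) | 93.5% |
| C: 0.85/1.0/1.2; 0.65, 0.50, 0.35 | 0.765 | 0.477 | 0.214 | 0.062 | 0.065 (16%) | 93.5% |
| D: 0.8/1.0/1.4; 0.75, 0.50, 0.30 | 0.938 | 0.454 | 0.190 | 0.092 | 0.092 (23%) | 91% |
| E: 1.2/1.0/0.85; correlations as C | 0.542 | 0.494 | 0.421 | 0.020 | not simulated | – |

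Percentages are of 0.4, and positive bias is attenuation. Simulated bias is from random-intercept REML fits with N = 600,000. Coverage is from 400 trials of 380 (Monte Carlo error about 1 point). Swapping the dropout patterns between the arms reverses the sign of Δ and so of the bias.

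With the same mechanism in both arms (log-odds −1.0 + 0.4·Y1), Δ is at most 0.016 and the simulated bias at most 0.005 in rows A to D. With an unstructured covariance the 3-month bias was at most 0.004 in every simulated setting. An extreme setting, with slopes of ±1 and about 70% against 60% retained, gave random-intercept bias of 0.08 (B) to 0.20 (D).

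**Interval width.** With complete data, the compound-symmetry variance is the average over visits, so model SE/true SE at a visit is √(mean variance)/s.

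- C at 12 months: √1.054/1.2 = 0.86.
- D at 12 months: √1.20/1.4 = 0.78.
- E at 12 months: √1.054/0.85 = 1.21, which is too wide.
- B at any visit: 1.00.
- At 3 months: 1.03 in C and E, 1.10 in D, so the complete-data interval at the primary visit is about right or slightly wide.

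Simulated 12-month coverage with the same dropout mechanism in both arms was 94.5% (B), 90% (C) and 86.5% (D). Differential dropout is not needed for this effect.

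**HCC and STAS-T.** Each has one post-baseline value once baseline is a covariate. Only the sum of the subject variance and the residual variance can then be estimated, so the stated random effect is not identifiable.

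**The case against.** The strongest reply is that the protocol never states a residual structure. A subject random effect can be combined with some residual structures, such as visit-specific variances; the R package and its options are not named; and covariance details are commonly left to a statistical analysis plan, which is not at hand. This stands in part. A reader might infer that the plan forces equal variances and correlations, and the text does not support that. It implies them on the usual reading. But an unstructured covariance over three visits already absorbs a random intercept, so an analysis plan could not simply add it to the stated model; it would have to replace the subject effect.

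A second reply is that the harm at 3 months needs two conditions together that the protocol does not describe: a non-exchangeable covariance, and dropout related to the post-assessment score differently by arm. This also stands. Arm-dependent dropout is plausible, because only assessors are described as blinded and only PM+ participants have weekly helper sessions, but that is inference. A reader might conclude that the primary estimate is biased, or biased towards no effect. Neither follows: the bias can be nil, and its sign depends on the dropout pattern.

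Third, a reader might infer that 12-month intervals are too narrow. That needs variance to rise by 12 months, and falling variance gives the opposite. In addition, 12 months is not the primary time point.

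None of these replies covers HCC and STAS-T, where the stated model does not fit the protocol's own schedule whatever is assumed.

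**Conclusion.** The point holds in conditional form. As written, and on the ordinary reading, the models imply equal variances and correlations over three unequally spaced visits.

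- **3-month effect:** essentially unbiased if dropout is random or follows the same mechanism in both arms. Otherwise it can shift by about 0 to 0.09 SD (0 to 23% of d = 0.4) under moderate arm-dependent dropout with a non-exchangeable covariance, with the sign set by the pattern. The extreme setting goes beyond this range, but I do not rest the conclusion on it.
- **Visit-specific intervals:** miscalibrated when variances differ by visit. At 12 months they are too narrow if variance rises (coverage about 90% and 86.5% in the two cases simulated with the same dropout mechanism in both arms) and too wide if it falls.
- **HCC and STAS-T:** the subject random effect cannot be estimated separately from residual error.

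All sizes rest on assumed SDs, correlations and dropout models. The point is worth correcting because the better model costs almost nothing, not because bias has been shown.

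**What to change.** For outcomes with two or more post-baseline assessments (HSCL-25 depression and anxiety, WHODAS 2.0, PCL-5, PSYCHLOPS and CSRI-based costs), replace the subject random effect with a repeated-measures model. It should have treatment, visit, treatment-by-visit, baseline and baseline-by-visit terms, and an unstructured residual covariance over the post-baseline visits. Read the 3-month contrast and the other visit contrasts from this model. State in advance a simpler covariance to use if it does not converge, for example heterogeneous Toeplitz with a robust variance.

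For HCC and STAS-T, use a linear model of the 3-month value on treatment and baseline.

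The cost is a few sentences in the Analysis section or the analysis plan, and six covariance parameters instead of two, which is minor with 380 participants. If compound symmetry is true nothing material is lost: in row A the 3-month standard errors of the two models differed by at most 0.001. No new data are needed and the sample size does not change.

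### The bootstrap 95% intervals promised around the ICERs cannot be interpreted when the effect difference is not clearly different from zero; net benefit from the same replicates avoids this

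*Protocol*

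**What the plan says.** The economic paragraph of the protocol's Analysis section plans ICERs "comparing changes in mean costs and primary outcomes from a payer and societal perspective between the two arms". The primary outcomes are depression and anxiety on the HSCL-25 (Primary outcomes section). If each is paired with each perspective, that gives 2 × 2 = 4 ratios.

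For uncertainty, the paragraph plans "Non-parametric bootstrapping analyses to derive 95% confidence intervals around ICERs". The same sentence adds that "cost-effectiveness acceptability curves will be generated showing the likelihood that PM+ would be cost-effective at different willingness-to-pay thresholds". It does not name the type of bootstrap interval, sets no condition under which an ICER interval is withheld, and does not mention net benefit.

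The Sample size section supplies the figures for judging how often the condition matters: a Cohen's d "effect size of 0.4 in the PM+ group at 3-months follow-up", 133 per group at 90% power and two-sided 5%, and a "30% attrition rate at the 3-month follow-up".

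**The concern.** An ICER is a cost difference divided by an effect difference. Its sign does not identify the situation: a negative ratio can mean cheaper and better or dearer and worse, and a positive ratio can mean dearer and better or cheaper and worse. The ratio also jumps between plus and minus infinity as the effect difference passes through zero.

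None of this matters while practically all replicates lie on one side of zero effect. Once a material share crosses, any interval built by ordering replicates on their ratio puts very unfavourable replicates at the end that reads as most favourable. A reader who sees a negative lower limit will tend to take it as possible cost saving with benefit, when the replicates beyond it may nearly all show higher cost and harm.

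Cost-effectiveness is named in the trial's objective beside effectiveness. The interval fails when the effect turns out small, which is when a clear statement of economic uncertainty is most needed.

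**Working it through.** **Inputs from the protocol (Sample size):** d = 0.4 at 3 months, two-sided α = 0.05, power 0.90, 133 per group, 30% attrition, 190 per group randomised.

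**1. Reproduce the plan's own figure.** The normal formula gives n = 2(1.960 + 1.282)²/0.4² = 131.3, so 132 per group. The t-based solution is 132.3, rounded up to 133. Inflation for attrition is 133/0.70 = 190 per group, 380 in total. Both agree with the protocol.

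**2. When do too many replicates cross zero?** In SD units, the standard error of the effect difference is √(2/133) = 0.1226. With an approximately normal bootstrap distribution, the share of replicates at or below zero effect is Φ(−z), where z is the observed effect divided by 0.1226. This share exceeds 2.5%, the size of one tail of a 95% interval, when z < 1.96. For a beneficial effect, that is when the 95% CI of the effect includes zero.

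**3. How often, by true effect?** The chance is Φ(1.96 − d/0.1226), for an unadjusted two-sample comparison and one outcome:

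| True d | d/0.1226 | Chance |
|---|---|---|
| 0.4 (design) | 3.26 | 9.6% |
| 0.3 (assumed) | 2.45 | 31% |
| 0.2 (assumed) | 1.63 | 63% |

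**4. What the interval looks like.** The protocol gives no cost figures, so these are assumptions for illustration: observed cost difference 600, cost SD 2000, no correlation between cost and effect. The standard error of the cost difference is 2000 × 0.1226 = 245. Percentile limits come from 4 million normal draws:

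| Observed effect (SD) | ICER per SD | Percentile 95% limits | Replicates with effect ≤ 0 |
|---|---|---|---|
| 0.4 | 1500 | about 280 to 4,400 | 0.06% |
| 0.2 | 3000 | about −15,300 to 24,900 | 5.1% |
| 0.1 | 6000 | about −54,000 to 58,000 | 21% |

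At 0.4 the interval is usable. At 0.2, about 5.1% of replicates are dearer and worse and 0.7% are cheaper and better. All of these have negative ratios, and about 99.9% of the replicates below the lower limit are dearer and worse. The lower limit is therefore set by the least favourable replicates. With smaller numbers of draws the extreme limits move by one or two thousand; the pattern does not change.

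**5. Coverage.** A simulation of the percentile interval (2,000 trials of 1,000 replicates, normal approximation, cost SD 2000, cost difference 0 to 1000) gave coverage of about 95% to 98% at true d = 0.4, 97% to 99% at 0.2, 96% to 99.6% at 0.1 and 92% to 99.8% at 0.05. The failure lies in the meaning of the limits and not chiefly in coverage.

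**6. Net benefit from the same replicates.** Take the observed effect of 0.2 and an illustrative threshold of 3000 per SD. Net benefit is 3000 × 0.2 − 600 = 0. Its standard error is √[(3000 × 0.1226)² + (2000 × 0.1226)²] = 442, and the 95% CI is about −867 to 867. It is an ordinary two-sided interval that crosses zero effect without difficulty.

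**The case against.** The strongest case against has four parts.

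- **The interval type is not stated.** The protocol does not say that replicates will be sorted and percentiles taken, and a SAP or health-economics plan may settle this. That is fair as to detail, and the absence of an interval type is not raised here. But the protocol does fix the quantity to be reported, an interval on the ratio, unconditionally. Percentile and bias-corrected forms both order replicates by that ratio, so choosing between them does not cure the problem.
- **The same sentence already plans acceptability curves.** Computed in the usual way by net benefit, they stay well defined at zero effect. This stands. A reader might infer that the whole cost-effectiveness objective collapses with the ICER interval; the protocol does not support that, because the curves carry the decision information independently. They do not stop a misleading interval from being printed next to them.
- **Coverage holds up.** A reader might infer that the intervals are invalid or have lost their error rate. The simulation does not bear that out: coverage stays near or above nominal apart from a modest shortfall at d = 0.05, and the affected intervals are very wide, so they do not suggest false precision. What remains is that their limits have no consistent direction.
- **The 10% is only the type II error restated.** That is correct. At the design effect the interval is usable in about 90% of trials per outcome, and the larger percentages need true effects below the 0.4 that the protocol calls conservative.

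The condition must also be put correctly. The difficulty is an effect not clearly different from zero in either direction; a clearly negative denominator is equally stable. The protocol makes no sign error.

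**Conclusion.** The point holds as a minor reporting matter. The unconditional promise of ICER intervals will produce limits that cannot be interpreted in about 10% of trials per outcome at d = 0.4, 31% at d = 0.3 and 63% at d = 0.2. These figures assume 133 analysed per arm, an unadjusted comparison and a normal approximation; a baseline-adjusted model with a smaller standard error would lower them. The numerical ICER intervals rest on assumed costs and serve only to show the mechanism. The primary effectiveness analysis, the sample size and the acceptability curves are unaffected.

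**What to change.** Amend the economic paragraph of the Analysis section in one or two sentences:

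- From the same bootstrap replicates, report incremental net benefit (threshold × effect difference − cost difference) with its 95% CI, over the willingness-to-pay range already planned for the acceptability curves.
- Show the cost-effectiveness plane for each outcome and perspective.
- Report the ICER as a point estimate, with an interval only when the 95% CI of the effect difference excludes zero.
- State the rule before unblinding, so that the summary is not chosen after a small effect has been seen.

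This needs no new data and no additional bootstrap run. The small cost is that net benefit is shown over a range of thresholds instead of as one number.

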Background: Syrian refugees face multiple hardships and adversities, which puts them at risk for the development of mental health problems. However, access to adequate mental health care in host countries is limited. The WHO has developed Problem Management Plus (PM+), a brief, scalable psychological intervention, delivered by non-specialist helpers, that addresses common mental disorders in people affected by adversity. This study is part of the larger STRENGTHS project, that aims to evaluate peer-refugee delivered psychological interventions adapted for Syrian refugees in Europe and the Middle East.

Objective: To evaluate the effectiveness and cost-effectiveness of the adapted peer-refugee delivered PM+ intervention among Syrian refugees with elevated levels of psychological distress in the Netherlands.

Methods: The adapted PM+ intervention will be tested in a randomized controlled trial (RCT) among Arabic-speaking Syrian refugees in the Netherlands aged 18 years and above with self-reported psychological distress (Kessler Psychological Distress Scale; K10>15) and impaired daily functioning (WHO Disability Assessment Schedule; WHODAS 2.0 >16). Participants ($N=380$) will be randomized into care as usual with PM+ (CAU/PM+, $n=190$) or CAU only (CAU, $n=190$). Baseline, 1-week post-intervention, 3-month and 12-month follow-up assessments will be conducted using tablet-assisted self-interviewing software with audio support. Primary outcomes are symptoms of depression and anxiety. Secondary outcomes are functional impairment, posttraumatic stress disorder symptoms, self-identified problems, anger, health and productivity costs, and hair cortisol concentrations. A process evaluation will be carried out to evaluate stakeholder views on barriers and facilitators to implementing PM+, as well as treatment dose and protocol fidelity.

Discussion: PM+ has proved effectiveness in other populations and settings. After positive evaluation of the PM+ intervention with Syrian refugees, the adapted manual and training

materials for individual PM+ will be made available through the WHO to encourage further replication and scaling up.

Trial registration: Trial registration Dutch Trial Registry, NL7552, registered prospectively on March 1, 2019. Medical Ethics Review Committee VU Medical Center Protocol ID 2017.320, 7 September 2017).

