An overview of all study measures is provided in Table 1. The WHODAS 2.0 is a generic instrument to assess health and disability and is used across all diseases, including mental, neurological and substance use disorders. It is easy to administer, applicable across cultures and can be used in all adult populations. The cross-culturally validated 12-item version covers difficulties that people experience due to their illness across six domains during the last 30 days (WHO, 2010). Difficulties are scored on a five-point Likert scale ranging from 1 (none) to 5 (extreme), before summation (range 12-60). In line with the earlier RCTs on PM+ a cut-off of >16 will be used (Bryant et al., 2017; Rahman et al., 2016). The WHODAS will also be administered as secondary outcome measure.

The K10 will be used to measure psychological distress. Ten items related to depression and anxiety are rated on a five-point Likert scale, before summation (range 10-50). The K10 has been validated in Arabic-speaking populations (Fassaert et al., 2009; Sulaiman-Hill & Thompson, 2010). In a study among Kurdish and Afghan (former) refugees and asylum seekers in New Zealand and Australia the following cut-off scores were used: 10-15.9 (low risk of psychological distress), 16-21.9 (moderate levels of distress consistent with a diagnosis of moderate depression and/or anxiety disorder), 22-29.9 (high level of distress) and 30 or more (possibility of very high or severe levels of distress) (Sulaiman-Hill & Thompson, 2010). In the current study, we will use a score of >15 as an indication of moderate to high levels of psychological distress.

Sociodemographic information (sex, age, education, work, marital status and time elapsed since displacement) will be collected through items based on the demographic section of the WHODAS 2.0.

[Insert Table 1 here]

Primary outcomes

The primary outcomes are the level of depression and anxiety 3 months after the post-assessment (or fifth PM+ session), as measured by the HSCL-25. The HSCL-25 is a self-report questionnaire for symptoms of psychological distress (Derogatis, Lipman, Rickels, Uhlenhuth, & Covi, 1974). Items are rated on a four-point (1-4) Likert scale. Item mean scores can be calculated for the depression (15 items) and anxiety subscales (10 items). The HSCL-25 has been used with Syrian refugees (e.g., Acarturk et al., 2016).

Secondary outcomes

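### Two primary outcomes share one unadjusted 0.05 threshold and one single-outcome power calculation, with no rule for combining their results

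*Protocol*

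**What the plan says.** The Abstract states: "Primary outcomes are symptoms of depression and anxiety". The Primary outcomes section agrees ("The primary outcomes are the level of depression and anxiety 3 months after the post-assessment") and describes two scores: "Item mean scores can be calculated for the depression (15 items) and anxiety subscales (10 items"). No HSCL-25 total is named as primary.

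The Sample size section gives one "effect size of 0.4 in the PM+ group at 3-months follow-up", without saying which outcome it refers to. It continues "Power calculations suggest a minimum sample size of 133" per group ("power = 0.90, α = 0.05, two-sided"), raised to 190 per group, 380 in total, for 30% attrition.

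The Analysis section describes the mixed model for a primary endpoint in the singular and rests the main conclusion on the intention-to-treat analysis. It closes with "Across all analyses, two-tailed tests will be reported with $p < 0.05". The protocol contains no alpha split, no ordering of the two outcomes, and no statement of whether one or both must be significant.

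**The concern.** Alpha 0.05 and power 0.90 were set for one test, but the outcome sections define two. With two tests, those figures have no definite meaning until a decision rule is stated. Under an either-outcome rule the error rate rises above 5%. Under a both-outcomes rule the power falls below the single-test figure.

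The Discussion links release of the manual and training materials through the WHO to a positive evaluation. If PM+ were significant on one subscale only, the protocol does not tell a reader whether that evaluation was positive.

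**Working it through.** **Inputs.** From Sample size: d = 0.4, 133 evaluable per group, two-sided alpha 0.05, power 0.90, 30% attrition. From Primary outcomes: two subscale scores. The correlation ρ between the subscales is not in the protocol. I assume 0.5 to 0.9 and show 0 as the limiting case.

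**1. The plan's own figure.** For an unadjusted two-group comparison the noncentrality is δ = 0.4 × √(133/2) = 3.262. The normal approximation gives power Φ(3.262 − 1.960) = 0.904. The noncentral t gives 0.899 at 132 per group and 0.901 at 133. Then 133 / 0.70 = 190 per group, 380 in total. The stated size reproduces for one outcome at the full 0.05.

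**2. Either outcome suffices, each tested at 0.05.** Familywise error = 1 − P(|Z₁| < 1.96 and |Z₂| < 1.96), with (Z₁, Z₂) bivariate normal with correlation ρ. At ρ = 0 this is 1 − 0.95² = 0.0975.

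**3. Both outcomes required, each at 0.05.** With d = 0.4 on each, power = Φ₂(δ − 1.96, δ − 1.96; ρ), where Φ₂ is the bivariate normal distribution function.

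| ρ (assumed) | Familywise error, either suffices | Power, both required |
|---|---|---|
| 0 | 9.75% | 0.816 |
| 0.5 | 9.1% | 0.838 |
| 0.7 | 8.3% | 0.852 |
| 0.8 | 7.8% | 0.861 |
| 0.9 | 7.0% | 0.873 |

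As ρ approaches 1, the columns tend to 5% and to the single-test power. Counting only false findings in favour of PM+, the error is 3.5% (ρ = 0.9) to 4.5% (ρ = 0.5), or 4.9% at ρ = 0, against 2.5% for one test.

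**4. Power under Holm.** At the first-step level of 0.025, power per subscale is Φ(3.262 − 2.241) = 0.846, or 0.843 by noncentral t. Over the whole procedure, a subscale passes if it clears 0.025, or if it clears 0.05 and the other clears 0.025. With d = 0.4 on both, that probability is 0.874 at ρ = 0.9, 0.886 at ρ = 0.5 and 0.895 at ρ = 0. Hochberg gives 0.888 to 0.898 over the same range. Under Holm, the probability that at least one subscale passes is 0.89 (ρ = 0.9) to 0.98 (ρ = 0).

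**The case against.** **A SAP could settle this.** A multiplicity procedure is often left to the SAP, and the closing sentence of Analysis could be read as a reporting convention. A SAP is not at hand, so a reader should not infer that the rule will be chosen after the data are seen; the protocol does not show that. But the protocol is not merely silent. It sets 0.05 for all analyses and spends the full 0.05 in the sample size. A SAP that split alpha would contradict the first and lower the power stated in the second.

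**A reader might infer that the trial is underpowered for both outcomes.** The protocol does not support that. The 0.82 to 0.87 belongs to the unadjusted sizing formula, whereas the planned model includes the baseline score. If d = 0.4 is in raw standard-deviation units, which is not stated, adjustment multiplies δ by 1/√(1 − r²), where r is the baseline-to-follow-up correlation (not given). At an assumed r = 0.3, both-required power is 0.86 to 0.90 for ρ from 0 to 0.9. At r = 0.5 it is 0.93 to 0.95. Randomizing household members together could pull the other way. This objection stands, so the power figure must be tied to the sizing assumptions.

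**A reader might also infer that the error nearly doubles.** That fits only near-zero correlation, which is implausible for two subscales of one questionnaire. Over 0.5 to 0.9 it is 1.8 to 1.4 times the stated 5%.

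**One score may have been meant.** The singular in Analysis and the single effect size fit that reading. If so, the multiplicity problem disappears, but the Abstract and Primary outcomes then need correcting. Nor does the Discussion say that one significant subscale would make the evaluation positive.

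**Conclusion.** The point holds at moderate severity. Two primary outcomes, one unadjusted threshold, one single-outcome sample size and a singular primary endpoint do not fit together, and no rule connects them.

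Under an either-outcome rule the familywise two-sided error is about 7.0% to 9.1%, not 5%. Under a both-outcomes rule the error is controlled, but power on the protocol's own sizing basis is about 0.84 to 0.87, not 0.90. Both ranges rest on an assumed subscale correlation of 0.9 to 0.5. The power range further assumes d = 0.4 on each subscale, 133 evaluable per group and no baseline adjustment. It would be lower if one effect were smaller, and could be higher under the planned model. It is therefore not an estimate of the power of the planned analysis.

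**What to change.** 1. Use the plural consistently, naming HSCL-25 depression and HSCL-25 anxiety at 3 months as the two primary outcomes in Abstract, Primary outcomes, Sample size and Analysis.
2. Test the two 3-month effects by Holm (or Hochberg) at familywise two-sided 0.05, with a claim allowed for each subscale that passes. Limit the unadjusted 0.05 to secondary and supportive tests.
3. Restate power under the sizing assumptions: 0.84 per subscale at the first-step level of 0.025, and about 0.87 to 0.90 per subscale over the whole procedure (Holm 0.87 to 0.89, Hochberg 0.89 to 0.90) if d = 0.4 holds on both. Do not print 0.90 for the second step as an unconditional figure, because that step is reached only when the other subscale has already passed.

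If a single HSCL-25 score was intended, name it as the sole primary outcome instead; 0.05 and 0.90 then stand. A both-required rule or a fixed order would also settle the error rate, each with its own power statement.

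The cost is a few sentences and a slightly lower stated power, with no added participants. For comparison, keeping 0.90 per subscale at a fixed 0.025 would need 156 evaluable per group, and 156 / 0.70 rounds up to 223 per group, 446 in total.
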